Study data identified in the schedule of events are collected, and source verified, on the electronic data capture tool: Axiom Fusion eClinical Suite (Axiom, Toronto, ON, Canada).

All study data will be formulated into regulatory compliant data sets to provide transparency, traceability, and integrity of trial analysis results from the collection source. Observed study data will be mapped to the CDISC Study Data Tabulation Model (SDTM) and serve as the source data from the trial. All study analyses will be completed using analysis data sets that are derived from the SDTM and follow the CDISC Analysis Data Model (ADaM) architecture. All planned analyses will be performed using the ADaM data sets developed for this study.

The following Implementation Guides will be referenced for the configuration of SDTM and ADaM datasets:

- SDTM Model 1.7 and SDTM Implementation Guide (SDTM IG) version 3.3 will be used.
- ADaM Model 2.1 and ADaM Implementation Guide (ADaM IG) version 1.3 will be used.

Statistical Summaries

All statistical tests in all phases of the study will be two-sided and p-values of less than or equal to 0.05 will be considered statistically significant.

All p-values will be rounded and displayed in 3 decimal places. If a p-value less than 0.001 occurs, it will be shown in tables as <0.001.

Descriptive summaries of variables will be provided where appropriate. For continuous variables, the number of non-missing values (n) and the median, mean, standard deviation, minimum, and maximum will be tabulated by treatment. For categorical variables, the counts and proportions of each value will be tabulated by treatment.

Data will be presented as listings where applicable. Data not patient to analysis according to this plan will not appear in any tables or graphs but will be included in the data listings.

4 Analyses Spanning Overall Study

For the below analyses, it will be summarized by overall.

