6.1 Efficacy Analysis

General Considerations

The FAS will be the primary data for efficacy analyses.

The primary efficacy estimand for the RW phase is

- Treatment regimen of interest: simufilam treatment for 6 months after OL treatment with simufilam for 12 months vs placebo treatment for 6 months after OL treatment with simufilam for 12 months
- Population:

As defined by inclusion / exclusion criteria

 Variable/Endpoint ADAS-Cog11 • Summary Measure

Difference between treatments in mean change from baseline (month 12) to endpoint (month 18, i.e. month 6 of RW Phase)

• Intercurrent events (ICE) strategy

The primary ICE of interest is early discontinuation of study drug, particularly for lack of efficacy. Given the RW phase is preceded by 12 months of OL treatment with simufilam, most patients entering the RW phase will have already demonstrated tolerability to simufilam; hence, discontinuations due adverse events are expected to be minimal. Discontinuations for lack of efficacy are likely given patients knowledge that the likelihood of being on placebo = 50%.

Discontinuations for lack of efficacy are consistent with a missing at random (MAR) mechanism and therefore a hypothetical strategy is relevant and meaningful. Therefore, a hypothetical strategy will be used to estimate the treatment effect as if the ICE if early discontinuation had not occurred.

Unless otherwise specified, for continuous endpoints that are scheduled to be assessed at > 1 postbaseline visit, mean changes from baseline will be analyzed using a restricted maximum likelihood (REML)-based repeated measures approach (MMRM). The MMRM analysis assumes an MAR mechanism. The analysis will include the categorical, fixed effects of treatment group and Visit, along with the continuous, fixed covariate of baseline value of the endpoint being analyzed (baseline), baseline MMSE score, and the interactions of treatment group, baseline, and baseline MMSE with Visit. An unstructured (co)variance structure will be used to model the within-patient errors. If this analysis fails to converge, the following structures will be tested in this order, with the first structure yielding convergence to be used as the appropriate structure for that variable: heterogeneous Toeplitz (TOEPH), heterogeneous compound symmetric (CSH), and compound symmetric (CS). The Kenward-Roger approximation will be used to estimate denominator degrees of freedom.

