Significance tests comparing mean changes from baseline by treatment group will be based on least-squares means. Significance of within-group mean changes from baseline will also be evaluated.

Biomarker Endpoints

Biomarker endpoints to be analyzed may include: 1) CSF A β 42, 2) CSF tau 3) CSF p- tau181, 4) CSF neurofilament light chain, 5) CSF neurogranin, 6) CSF sTREM2, 7) CSF YKL40 8) CSF 1) plasma neurofilament light chain, 2) plasma GFAP.

Plasma biomarker data may be analyzed with the MMRM model described above.

Clinical Endpoints

The ADAS-Cog11 will be analyzed using the MMRM model described above.

7 Analysis of Follow up to Randomized Withdrawal Phase (Openlabel)

The follow up phase is defined as beginning after the month 18 Visit through the month 24 assessment. The following efficacy analyses will be applied to the follow up data.

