7.1 Efficacy Analysis

The efficacy analyses will be ADAS-Cog11 using the FAS. The first analysis will be change in ADAS-Cog11 from Month 12 to Month 24 by Treatment, Visit, and mild vs. moderate status. The second analysis will be change in ADAS-Cog 11 from Day 1 to Month 24 by Treatment (i.e. continuous vs. interrupted), Visit, and mild vs. moderate status (mild vs. moderate here based on OL baseline).

The primary comparison of interest from these analyses is the magnitude of the treatment effect at month 18 vs month 24. Maintenance of the treatment effect seen at the end of the RW phase (month 18) throughout the follow up phase (month 24) when all patients are on active drug would be consistent with a disease modifying effect. In contrast, appreciable diminution of the treatment effect when placebo-treated patient switch to active drug would be consistent with a symptomatic treatment effect.

Approvals: 8

[name] Lead Biostatistician **Axiom Real-Time Metrics**

Electronically signed by: [name] Reason: I have reviewed this document Date: Dec 11, 2023 19:14 EST

11-Dec-2023

Date

Electronically signed by: [name] , Reason: I am the Author of [name] this document Date: Dec 11, 2023 11:04 EST

[name] Lead Biostatistician Pentara Corporation

11-Dec-2023

Date

Electronically signed by: [name] Reason: I approve this document Date: Dec 11, 2023 14:29 MST [name] CEO Pentara Corporation

[name]

11-Dec-2023

Date

[name]

[name]

SVP, Neuroscience Cassava Sciences, Inc.

Electronically signed by: [name] Reason: I approve this document Date: Dec 11, 2023 08:46 CST

Electronically signed by: [name] Reason: I have reviewed this

document Date: Dec 11, 2023 09:15 CST

11-Dec-2023

Date

[name] Assistant VP, Clinical Operations Cassava Sciences, Inc.

11-Dec-2023

Date

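### SAP 7.1 reads a mechanism into the Month 18 versus Month 24 effect without requiring a significant Month 18 result or an interval on the change

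*SAP*

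**What the plan says.** SAP 7.1 covers the open-label follow-up after the randomized withdrawal (RW) phase. It sets two ADAS-Cog11 analyses on the FAS. One runs from Month 12: "The first analysis will be change in ADAS-Cog11 from Month 12 to Month 24 by Treatment, Visit, and mild vs. moderate status". The other runs from Day 1. It then states: "The primary comparison of interest from these analyses is the magnitude of the treatment effect at month 18 vs month 24".

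Two readings follow. "Maintenance of the treatment effect seen at the end of the RW phase (month 18) throughout the follow up phase (month 24", once all patients are on active drug, would be consistent with a disease-modifying effect. By contrast, "appreciable diminution of the treatment effect when placebo-treated patient switch to active drug would be consistent with a symptomatic treatment effect".

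The Month 18 effect is defined and tested elsewhere. SAP 6.1 gives the summary measure as "Difference between treatments in mean change from baseline (month 12) to endpoint (month 18, i.e. month 6 of RW Phase", and adds: "Significance tests comparing mean changes from baseline by treatment group will be based on least-squares means". SAP 3.2 sets the level: "All statistical tests in all phases of the study will be two-sided and p-values of less than or equal to 0.05". Section 7.1 does not refer to that test. It gives no threshold for maintenance or for appreciable diminution, and it names no contrast, standard error or interval for the change between the two visits. The SAP text specifies no confidence interval for any comparison.

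**The concern.** The mechanistic reading compares two estimates, and nothing in 7.1 requires the first to be distinguishable from zero. If simufilam and placebo patients differ by chance at Month 18, the same patients in the same arms are measured again at Month 24 against the same baseline. Positive correlation then makes the gap tend to persist, and persistence is the pattern that 7.1 associates with disease modification.

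With no interval on the change, the reader is left to compare two point estimates or two p-values. Neither shows whether the data can tell retention from loss.

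This is the only place in the SAP where a disease-modification reading is set out. SAP 1.1 says results may be used in regulatory submissions, manuscripts and guidance for the Phase 3 programme.

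**Working it through.** The documents give no SD, correlation, effect size, power or retention threshold for this comparison, so there is no planned figure to reproduce.

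**Inputs from the documents**
- Two-sided 0.05 (SAP 3.2) and 1:1 allocation (SAP 2.2).
- SAP 2.5: 220 enrolled, 43 dropped out in the open-label phase, 21 did not continue. 220 − 43 − 21 = 156, or 78 per arm. The number randomized is not stated.

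**Assumptions**
- Correlation r of the Month 18 and Month 24 effect estimates: 0.5 to 0.8.
- Ratio k = SD at Month 24 / SD at Month 18: 1.0 to 1.2.
- SD of ADAS-Cog11 change: 5 to 8 points.
- No further dropout, which would widen the intervals.

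Let D18 and D24 be the estimated advantage of simufilam in points.

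**Step 1. Carry-over of a chance difference.** With no true effect, E[D24 | D18] = r × k × D18.
- Lowest: 0.5 × 1.0 = 0.50.
- Highest: 0.8 × 1.2 = 0.96.

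This does not depend on sample size or on the SD itself.

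**Step 2. How often noise looks retained.** For illustration only, call a favourable gap maintained if at least half of it remains. That cut is not in the SAP. In a bivariate-normal simulation with no true effect:
- a favourable Month 18 gap keeps at least half its size in 50% to 68% of cases, which is 25% to 34% of all null trials;
- if Month 18 must also be significant in favour of simufilam, this falls to 1.2% to 2.3% of null trials.

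**Step 3. Precision of the change.** The SE of D24 − D18 is √(SE18² + SE24² − 2·r·SE18·SE24). Its 95% half-width, divided by the smallest significant Month 18 effect (1.96 × SE18), is √(1 + k² − 2rk).
- r = 0.8, k = 1.0: √(2 − 1.6) = 0.63.
- r = 0.5, k = 1.2: √(2.44 − 1.2) = 1.11.

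At 78 per arm with equal SDs, the half-width runs from 1.0 point (SD 5, r = 0.8) to 2.5 points (SD 8, r = 0.5). A 2-point effect that halves loses 1 point, about equal to or below that half-width throughout. An interval that includes 0 is therefore weak evidence of retention. Among null trials with a favourable Month 18 gap and equal SDs, a test of the change is non-significant in about 96%.

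**Step 4. What a Month 18 condition costs.** SE18 = SD × √(2/78). The probability that a true 2-point effect is significant is P(Z > 1.96 − 2/SE18).

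| SD | SE18 | 1.96 − 2/SE18 | Probability |
|---|---|---|---|
| 5 | 0.80 | −0.54 | 0.70 |
| 6 | 0.96 | −0.12 | 0.55 |
| 7 | 1.12 | 0.18 | 0.43 |
| 8 | 1.28 | 0.40 | 0.34 |

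**Step 5. Selection.** Among trials that meet the condition, the mean Month 18 estimate is 2 + SE18 × φ(c)/(1 − Φ(c)), with c = 1.96 − 2/SE18.
- SD 5: 2 + 0.80 × 0.49 = 2.4.
- SD 8: 2 + 1.28 × 1.07 = 3.4.

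If the true effect is fully kept, the average apparent loss is (1 − rk) times the excess over 2. That runs from 0.04 × 0.39 = 0.02 points (SD 5) to 0.5 × 1.37 = 0.7 points (SD 8).

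**The case against.** The best reply is that the harm needs a reader to go further than the SAP does. Section 7.1 speaks of an effect already seen at Month 18, which may presuppose that 6.1 found one. The wording says only that a pattern would be consistent with a mechanism. SAP 1.3 lists the 24-month comparison of continuous and interrupted dosing among exploratory objectives, and no decision rule depends on it. These points stand and limit the severity. They do not close the gap, because an effect seen can mean any favourable point estimate.

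A second reply is that the machinery already exists. The 6.1 MMRM is the default: "Unless otherwise specified, for continuous endpoints that are scheduled to be assessed at > 1 postbaseline visit", and it contains treatment-by-visit terms, so the contrast is one linear combination of its estimates. That is fair, and it is why the fix is cheap. But the tests that 6.1 asks for are between-group differences and within-group changes. Neither is the difference between the Month 24 and Month 18 effects.

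A reader might also infer that 7.1 contradicts section 6, because it names only treatment, visit and mild/moderate status and counts from Month 12. The documents do not support that. Section 6.1 itself uses Month 12 as shorthand for the RW baseline defined in section 6, and 7.1 does not rule out the default model.

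Finally, SAP 1.2 says earlier SAP versions were used for the RW analyses. A condition added to 7.1 is therefore an interpretive safeguard, not prespecified error control.

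**Conclusion.** The concern holds in a limited form. Section 7.1 neither ties its disease-modifying or symptomatic reading to a significant Month 18 result nor asks for an interval on the change in effect. A chance difference, or a change too imprecise to classify, can therefore be given a mechanistic label.

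The direction of the bias needs only a positive correlation between the visits. Its size (50% to 96% expected carry-over) rests on the assumed correlation and SD ratio.

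A reader might take the 25% to 34% of null trials as the plan's false-positive rate for disease modification. It is not: it uses a 50% retention cut that the SAP does not contain, and the SAP sets up no such claim. Nor do the documents show that the sponsor intends to read a non-significant Month 18 difference as an effect. The text simply does not prevent it. This is an inexpensive change that should be made, not a flaw in the primary RW analysis.

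**What to change.** In SAP 7.1:

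1. Give a disease-modifying or symptomatic reading only if the 6.1 Month 18 comparison significantly favours simufilam. Otherwise report the Month 18 and Month 24 estimates descriptively.
2. From one MMRM (the 6.1 model extended to Months 21 and 24, with the RW baseline as defined in section 6), report the Month 18 effect, the Month 24 effect and the Month 24 minus Month 18 contrast, each with a 95% confidence interval. Base the wording on those limits.
3. State that a contrast interval that includes 0 does not by itself show maintenance. Where the limits are compatible with both retention and substantial loss, call the result inconclusive.

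The cost is SAP wording, one contrast and three intervals, using data that the plan already collects. The price is that a real effect may go without a mechanistic reading: at 78 per arm a true 2-point effect meets the condition in about 34% (SD 8) to 70% (SD 5) of trials. The condition also inflates the Month 18 estimate among the trials that meet it, which pushes the contrast towards apparent loss. Say so where the contrast is interpreted.
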